## **PROTOCOL SYNOPSIS**

### **Trial Title:**

A Phase 2 Trial of SRF617 in Combination With AB928 (Etrumadenant) and AB122 (Zimberelimab) in Patients With Metastatic Castration-Resistant Prostate Cancer

### **Protocol Number:** SRF617-201

### **Phase:** 2

**Study Drugs:** SRF617 in combination with etrumadenant (AB928) and zimberelimab (AB122)

### **Trial Population:**

This open-label Simon 2-stage trial will enroll approximately 40 patients with metastatic castration-resistant prostate cancer (mCRPC) who have progressed on or after prior androgen receptor signaling inhibitor (ARSI) therapy. All patients will receive SRF617 in combination with etrumadenant and zimberelimab.

### **Duration:**

Patients will continue to receive study drug for up to 2 years or until documented disease progression or unacceptable toxicity. Patients may remain on study drug longer than 2 years with agreement from the trial Investigator and Sponsor. All patients will have a Safety Follow-up visit after the last dose of study drug (SRF617, etrumadenant, and/or zimberelimab).

### **Trial Centers:**

Enrollment is anticipated at approximately 15 sites in the United States and Canada.

### **Trial Design:**

This Phase 2, open-label, safety and preliminary efficacy trial in patients with mCRPC will employ a Simon 2-stage design with an integrated safety lead-in for the triplet combination of SRF617, etrumadenant, and zimberelimab. Cycles are 28 days in duration. Stage 1 will enroll approximately 17 patients, including the Safety Lead-in that will initially treat 6 patients. After the first 6 patients have been enrolled, enrollment will be paused until these patients have received 1 cycle of the triplet combination and the Safety Review Committee (SRC) has reviewed the aggregate safety data. Once the SRC deems it safe to proceed, an additional 11 patients will be enrolled. Based on an evaluation of safety and response data, the trial will proceed to the Stage 2 expansion if  $\geq 1$  radiographic complete response (CR)/partial response (PR) or 2 prostate-specific antigen (PSA) responses (defined as a  $\geq 50\%$  decline [PSA50]) according to the Prostate Cancer Working Group 3 (PCWG3) criteria are observed in 17 evaluable patients. An additional 23 patients will be enrolled in Stage 2 for further evaluation of the safety and efficacy of the combination. Tumor biopsies are optional; they will be performed to explore potential biomarkers of response to the combination in patients who consent to the procedure, who have non-bone metastases amenable to biopsy, and for whom the procedure is deemed safe.

### **Safety Review Committee**

The SRC will be composed of a medical representative from the Sponsor, a Medical/Safety Monitor from the Contract Research Organization supporting the trial (if applicable), and all

Principal Investigators (or their specified delegates) at each of the enrolling sites. The SRC will meet regularly throughout the trial to review all available safety, pharmacokinetics (PK), and preliminary efficacy data. The SRC may recommend investigating intermediate doses or alternative schedules for administration of SRF617 to optimize combination dose determination. The SRC may recommend halting or stopping the trial at any time based on a comprehensive review of all clinical data.

### **Stage 1 Safety Lead-in**

Once the first 6 patients in Stage 1 have received 1 cycle of the triplet combination, the SRC will review the aggregate safety data. To be considered evaluable for the Safety Lead-in, patients must have completed at least 50% of the prescribed doses of all 3 drugs during the review period (Day 1-28 = Cycle 1) and must not have discontinued treatment during Cycle 1 for reasons other than drug-related adverse events (AEs). For example, patients who discontinued study treatment during Cycle 1 for progressive disease or for patient or physician preference but without experiencing a Grade  $\geq 3$  related toxicity would not be considered fully evaluable for the Safety Lead-in and would be replaced. A ‘related’ toxicity is defined as those toxicities assessed by the Investigator to be possibly, probably, or definitely related to any study drug.

This analysis set will be used to assess the preliminary safety of the triplet therapy.

The following safety stopping rule will also be applied during the Safety Lead-in: If 2 or more of these 6 patients experience a Grade  $\geq 3$  related AE (with the exception of toxicities listed in the table below), any treatment-related toxicity that causes the participant to discontinue treatment during Cycle 1, or prolonged delay (>14 days in initiating Cycle 2 due to toxicity), the trial will be halted for SRC review.

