### Analysis Sets

The Safety Lead-in Evaluable Analysis Set is defined as the first 6 patients enrolled in the Simon stage 1 who either experienced a Grade  $\geq 3$  related AE during the first cycle of therapy (D1-28) or who completed at least 50% of the prescribed combination therapy doses. The SRC will review the aggregate safety data of these 6 patients during Cycle 1 and must clear the trial for further enrollment of the remaining 11 patients in Stage 1. The goal of the safety evaluation for the triplet is to evaluate for any signal of unexpected or increased toxicities when given together that would not be observed with any agent alone. As such, a Grade  $\geq 3$  toxicity known to be associated with any of the 3 study drugs' established safety profiles would not be considered concerning.

The Safety Analysis Set is defined as all patients who received any amount of study drug. This analysis set will be the primary analysis set for all safety endpoints, excluding safety lead-in evaluation. This analysis set will be used to assess the tolerability of SRF617 in combination with etrumadenant and zimberelimab.

The Response-Evaluable Analysis Set is defined as all patients at Baseline who received study drug and had at least 1 post-Baseline response assessment or who discontinued the treatment phase because of radiographic or symptomatic disease progression (including death caused by disease progression) within 6 weeks (+ 2 week window) of the first dose of study drug. This analysis set will be the primary analysis set for the primary efficacy endpoint and other efficacy endpoints. ORR will be assessed separately by PCWG3 criteria as well as RECIST v1.1. For the primary composite response endpoint of PSA50 or CR/PR, ORR will be measured using PCWG3 criteria. PSA response is defined as a confirmed PSA decrease from Baseline of 50% or more based on 2 consecutive assessments measured 3 to 4 weeks apart. Changes in PSA across the trial period will be described using a waterfall plot. Swimmer plots will be used to describe time on trial including timing and incidence of treatment past progression, timing of serious adverse events (SAEs) or adverse events of special interest (AESIs), and may be used to reflect the concept of no longer clinically benefiting.

The Intent-to-Treat Analysis Set is defined as all enrolled patients who received any amount of study drug.

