### **4.1. Stage 1**

Stage 1 will enroll approximately 17 patients, including the Safety Lead-in that will initially treat 6 patients. After the first 6 patients have been enrolled, enrollment will be paused until these patients have received 1 cycle of the triplet combination and the SRC has reviewed the aggregate safety data. Once the SRC deems it safe to proceed, an additional 11 patients will be enrolled.

To be considered evaluable for the Safety Lead-in, patients must have completed at least 50% of the prescribed doses of all 3 drugs during the review period (Day 1-28 = Cycle 1) and must not have discontinued treatment during Cycle 1 for reasons other than drug-related AEs. For example, patients who discontinued study treatment during Cycle 1 for progressive disease or for patient or physician preference but without experiencing a Grade  $\geq 3$  related toxicity would not be considered fully evaluable for the Safety Lead-in and would be replaced. A ‘related’ toxicity is defined as those toxicities assessed by the Investigator to be possibly, probably, or definitely related to any study drug.

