#### **9.2.1. Safety Lead-in Evaluable Analysis Set**

The Safety Lead-in Evaluable Analysis Set is defined as the first 6 patients enrolled in the Simon Stage 1 who either experienced a Grade  $\geq 3$  related AE during the first cycle of therapy (D1-28) or who completed at least 50% of the prescribed combination therapy doses. The SRC will review the aggregate safety data of these 6 patients during Cycle 1 and must clear the trial for further enrollment of the remaining 11 patients in Stage 1. The goal of the safety evaluation for the triplet is to evaluate for any signal of unexpected or increased toxicities when given together that would not be observed with any agent alone. As such, a Grade  $\geq 3$  toxicity known to be associated with any of the 3 study drugs' established safety profiles would not be considered concerning.

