3.2 Safety Lead-in Evaluable Analysis Set

The Safety Lead-in Evaluable Analysis Set is defined as the first 6 patients enrolled in Stage 1 who completed at least 50% of the prescribed combination therapy doses during the first cycle of therapy (D1–28) or who received less than 50% of the prescribed combination therapy doses due to any Grade ≥ 3 related AE (including relationship to SRF617, Etrumadenant and/or Zimberelimab as Definite, Probable, and/or Possible) during the first cycle of therapy (D1–28).

This analysis set will be used to assess the preliminary safety of the combination therapy in the Safety Lead-in Period.

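### A Grade 1-2 related toxicity that ends treatment before half the Cycle 1 doses counts in the lead-in stopping rule, but the patient fits none of the definitions of the evaluable six

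*Protocol*

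**What the plan says.** **The rule.** It begins "If 2 or more of these 6 patients experience a Grade" 3 or higher related event outside the listed exceptions. It then adds two further kinds of event: "any treatment-related toxicity that causes the participant to discontinue treatment during Cycle 1", and a toxicity-related delay of more than 14 days in starting Cycle 2. If the count is reached, the trial is halted for SRC review. The Synopsis and Section 4.6 word the rule alike.

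**The set.** There are three definitions:

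- Synopsis (Stage 1 Safety Lead-in) and Section 4.1: "patients must have completed at least 50% of the prescribed doses of all 3 drugs during the review period", and in addition no discontinuation in Cycle 1 except for drug-related adverse events. Patients who stop for progression or preference without a Grade 3 or higher related toxicity are given as an example of those who "would not be considered fully evaluable for the Safety Lead-in and would be replaced".
- Synopsis (Analysis Sets) and Section 9.2.1: the first six enrolled with a Grade 3 or higher "related AE during the first cycle of therapy (D1-28) or who completed at least 50% of the prescribed combination therapy doses".
- SAP 3.2: the first six who completed at least 50% of doses in Cycle 1, or who "received less than 50% of the prescribed combination therapy doses due to any Grade" 3 or higher related event.

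Section 9.2.1 then has the SRC review the data of the six patients it has just defined and clear the remaining 11 of Stage 1. SAP Section 11 bases the lead-in analysis on the SAP 3.2 set.

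**The concern.** The second kind of event in the rule has no grade limit, so it covers intolerance that ends treatment without reaching Grade 3. Every route into the evaluable set for a patient below half his doses either does not exist (4.1) or requires Grade 3 or higher (9.2.1, SAP 3.2). A patient can therefore have an event that the rule counts and still be outside the set on which the rule appears to be scored. His place would go to the next patient who qualifies.

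At stake is whether the lead-in trigger registers early intolerance. It is the only numerical safety trigger in the plan, and Protocol 10.7 provides for no independent data monitoring committee. This point is separate from the three definitions differing among themselves, because on this patient they all give the same answer.

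**Working it through.** **Step 1. When is 50% reached?** Section 4.4 gives the Cycle 1 doses: SRF617 on Days 1 and 15 (2 doses), zimberelimab on Day 1 (1 dose), etrumadenant daily (28 doses). On Day 1 SRF617 reaches 1/2 = 50% and zimberelimab 1/1 = 100%, so etrumadenant decides. Assuming no missed doses and all drugs stopped together:

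| Last dose | Etrumadenant | All doses pooled | At least 50%? |
|---|---|---|---|
| Day 13 | 13/28 = 46.4% | (13+1+1)/31 = 48.4% | No |
| Day 14 | 14/28 = 50.0% | (14+1+1)/31 = 51.6% | Yes |

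The gap therefore covers a last dose on Days 1 to 13, whether doses are counted per drug or pooled. From Day 14 the patient is evaluable and is counted.

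**Step 2. Test one patient against each text.** He stops all drugs on Day 10 for a Grade 2 related toxicity.

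| Text | Result |
|---|---|
| Stopping rule (Synopsis, 4.6) | Counts as one event |
| Synopsis and 4.1 | Reason for stopping is tolerated, but the 50% condition is joined by *and*, so he is not evaluable |
| Synopsis and 9.2.1 | Neither Grade 3 or higher nor 50% of doses: not evaluable |
| SAP 3.2 | Below 50%, but not because of a Grade 3 or higher event: not evaluable |

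**Step 3. Effect on the trigger.** The documents give no operating characteristics for the lead-in (SAP Section 14 says safety monitoring has no statistical support), so there is no stated figure to reproduce, and all rates below are assumptions. Let q be the proportion of patients with a counted event, and e the proportion whose only counted event is a Grade 1-2 toxicity ending treatment before half the doses.

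- If they are counted: P(at least 2 of 6) = 1 − (1−q)^6 − 6q(1−q)^5.
- If they are replaced: the same formula with q′ = (q − e)/(1 − e).

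For q = 0.30: 1 − 0.1176 − 0.3025 = 0.580. For e = 0.10: q′ = 0.20/0.90 = 0.222, which gives 0.399.

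| q | e | q′ | Counted | Replaced |
|---|---|---|---|---|
| 0.30 | 0.01 | 0.293 | 58.0% | 56.4% |
| 0.30 | 0.02 | 0.286 | 58.0% | 54.8% |
| 0.30 | 0.05 | 0.263 | 58.0% | 49.7% |
| 0.30 | 0.10 | 0.222 | 58.0% | 39.9% |
| 0.40 | 0.10 | 0.333 | 76.7% | 64.9% |
| 0.10 | 0.05 | 0.053 | 11.4% | 3.6% |

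**The case against.** **The six may not be the evaluable six.** Section 4.6 names no analysis set, and the Synopsis and 4.1 also speak of the first six patients enrolled. On that reading the event counts. This stands as an ambiguity. Against it, the Synopsis places the rule directly after the evaluability text, and 9.2.1 ties SRC clearance to the evaluable set. If the first six treated are meant, the rule still looks at a different group from the one that 9.2.1 has the SRC review.

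**Replacement is inferred.** A reader might infer that the protocol orders this man to be replaced. It does not: its example covers progression and preference only. Replacement follows because the set holds six qualifying patients and he is not one. Moreover, read literally, 4.1 would also exclude a patient below 50% with a Grade 3 or higher related event, whom 9.2.1 keeps and SAP 3.2 keeps if that event caused the shortfall. The literal wording may therefore not be what was intended, which is a reason to reconcile it.

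**The SRC reviews anyway.** Enrollment pauses after six patients, and SRC clearance is required whether or not the rule triggers. The SRC sees all available safety data and may recommend halting at any time (4.3). A trigger only halts the trial for that review. The man also stays in the Safety Analysis Set. So a reader might infer that early intolerance is lost from view or that 11 more patients would be cleared unsafely; the documents support neither. What is affected is the prespecified count.

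**The rates may be small.** Tables 7 and 10 mostly continue, hold or reduce at Grade 1-2, with the combined transaminase and bilirubin criterion as an exception. This stands, and it is why the table above starts at 1%.

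**A mirror-image flaw.** A reader might infer that the set is equally wrong in the other direction, because 9.2.1 admits a barely exposed patient with a Grade 3 or higher event that Table 4 exempts, who then counts as event-free. Little of this survives. If that toxicity ended treatment or delayed Cycle 2 by more than 14 days, the rule sentence counts it on another ground, since it attaches the exceptions only to the Grade 3 or higher part. SAP 3.2 also requires the event to have caused the shortfall. What is left is, for example, a temporary hold with a timely Cycle 2, or under 9.2.1 an early stop for an unrelated reason.

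**Conclusion.** The mismatch is in the text: the rule counts an event that all three set definitions leave out. It is confined to patients who stop all drugs for a Grade 1-2 related toxicity with a last dose by about Day 13. One such event is only one of the two needed for the trigger.

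The size cannot be known from the documents. At an assumed 30% event rate, the chance of reaching the trigger falls by about 3 percentage points if 2% of patients are lost this way (58.0% to 54.8%) and by about 18 if 10% are (58.0% to 39.9%). These figures assume independent patients, scoring on the evaluable six, and replacement. They are chances of meeting the trigger, not of stopping the trial, and should not be read as estimates for this trial.

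The SAP (1.1 and Section 2) records that the sponsor closed enrollment with 15 patients treated, more than the six of the lead-in. The remaining practical effect is on which patients appear in the lead-in safety analysis under SAP 3.2 and Section 11.

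**What to change.** Reconcile the Synopsis, Protocol 4.1, 4.6 and 9.2.1, and SAP 3.2, so that the set is built from the events the rule counts:

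- State that any patient with an event counted in Section 4.6 is evaluable and is not replaced, whatever the grade or the doses received.
- Say in 4.6 which six patients the rule is scored on.
- For patients without such an event, keep the existing condition on discontinuation for reasons other than adverse events.
- Settle openly on one wording of the dose threshold (each of the three drugs, or the combination as a whole), and on the status of a patient below it whose only event is an exempt Grade 3 or higher toxicity.

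The list of counted events stays with the clinical team. With enrollment closed, the change that still matters is in SAP 3.2. The lead-in report should also list any early-treated patient left out of the set, with the reason.

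The cost is a few sentences. In a lead-in still enrolling, the downside would be a slightly higher chance that the rule triggers an SRC review.

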### **Stopping Rule Exceptions**

|   |  |
|---|--|
| The following Grade $\geq 3$ toxicities considered at least possibly related to study treatment would not be considered to meet criteria for a safety stopping rule: |  |
| Nausea  |  |
| Vomiting  | Any Grade $\geq 3$ event responding to supportive treatment within 3 days  |
| Diarrhea  |  |
| Fatigue   | Grade $\geq 3$ lasting < 7 days  |
| Asymptomatic amylase/lipase elevations  | Grade $\geq 3$ lasting any duration if asymptomatic/ no clinical signs of pancreatitis   |
| Thyroid function abnormalities (eg, hypo- or hyperthyroidism)   | Grade $\geq 3$ lasting any duration if can be controlled with treatment such as thyroid supplementation or beta blockade                   |
| Rash  | Grade $\geq 3$ recovering to Grade 1 with treatment (ie, steroids) within 7 days   |
| Alopecia  | Grade $\leq 2$ lasting any duration  |
| Non-hematologic laboratory abnormalities  | Clinically nonsignificant, treatable, or reversible laboratory abnormalities including liver function tests, electrolytes, uric acid, etc. |

### **Adverse Event Monitoring**

All patients will be monitored continuously for toxicity while on study drug. AE severity will be assessed using the National Cancer Institute Common Toxicity Criteria for Adverse Events

(NCI-CTCAE) version 5.0, or higher. If a patient has an AE of a particular severity or an AE at least possibly related to study drug, then dose modifications should be made according to the guidelines set forth in the trial protocol.

**Trial Objectives:**

Primary Objective:

- To evaluate the preliminary efficacy of SRF617 administered in combination with etrumadenant and zimberelimab as determined by objective response and PSA decline
- To evaluate the safety and tolerability of the combination

Secondary Objectives:

- To evaluate additional preliminary efficacy parameters of the combination including objective response rate (ORR), PSA response, clinical benefit, duration of response, and radiologic progression-free survival (PFS)
- To evaluate the PK of SRF617 when administered in combination with etrumadenant and zimberelimab
- To characterize additional safety parameters including development of antidrug antibodies (ADAs) and symptomatic skeletal events (SSEs)

Exploratory Objectives:

- Explore potential biomarkers of response and/or safety of the combination
- Explore the effects of the triplet on peripheral blood immune cell subsets and circulating serum cytokines and chemokines
- Explore the biological effects of the triplet on tumor cells and immune cell populations in the tumor microenvironment
- Explore germline DNA polymorphic variations in relation to the PK, pharmacodynamics, safety, and/or preliminary efficacy
- Explore correlations between prostate cancer biomarkers in tumors with biomarkers in serum in patients who undergo tumor biopsy
- Explore correlations between prostate cancer biomarkers in tumors with clinical response parameters in patients who undergo tumor biopsy

**Trial Endpoints:**

Primary Endpoint:

- The proportion of patients with a response, defined as PSA50 response ( $\geq 50\%$  decline) and/or radiographic objective response of CR or PR per PCWG3 criteria
- Incidence and severity of AEs

Secondary Endpoints:

- ORR per PCWG3 criteria, ORR per Response Evaluation Criteria in Solid Tumors (RECIST) v1.1, duration of response, disease control rate, PSA50 response, PSA decline  $\geq 30\%$  (PSA30) response, time to PSA progression, radiographic PFS, and landmark PFS rate at 6 and 12 months

- Serum concentrations of SRF617
- Percentage of patients with ADAs to SRF617
- Incidence of SSEs

Exploratory Endpoints:

- Changes in selected blood and tumor tissue biomarkers
- Germline DNA polymorphic sequence variations in relation to the PK, pharmacodynamics, safety, and/or preliminary efficacy of SRF617
- Serum prostatic acid phosphatase (PAP) levels
- PAP expression levels in tumors in patients who undergo tumor biopsy
- Programmed death-ligand 1 (PD-L1) and CD39 expression levels in tumors in patients who undergo tumor biopsy

**Inclusion Criteria:**

All patients must meet the following criteria for inclusion:

1. Males  $\geq$  18 years of age on the day of signing informed consent.
2. Metastatic CRPC with castrate levels of testosterone ( $\leq$  50 ng/dL or  $\leq$  1.7 nmol/L).
3. Eastern Cooperative Oncology Group (ECOG) performance status of 0 to 1.
4. Must have progressed (by PSA or radiologic criteria) during or following treatment with a novel ARSI (eg, abiraterone, enzalutamide, apalutamide, darolutamide), which may have been given for either hormone-sensitive prostate cancer or CRPC.
5. Must have received 1 to 2 prior lines of taxane chemotherapy, unless the physician and patient believe the patient is medically ineligible or the patient refuses (ineligibility or refusal must be documented in the source documents).
6. Must have progressed by PSA or radiologic criteria on or during last therapy for prostate cancer.
7. Measurable or non-measurable disease as per radiographic evaluation. Lesions situated in a previously irradiated area are considered evaluable if progression has been demonstrated in such lesions since radiation.
  - Note: If disease is considered non-measurable, a minimum PSA of 1 ng/dL is required with at least 1 confirmed rise at a minimum of a 1-week interval.
8. Washout period from the last dose of previous anticancer therapy (chemotherapy, biologic, or other investigational agent) to the first dose of study drug must be  $>$  5 times the half-life of the agent or  $>$  21 days, whichever is shorter. The washout period for palliative radiation (defined as  $\leq$  2 weeks of radiation) to non-central nervous system (CNS) disease is  $>$  7 days.
9. Resolution of non-immune-related AEs secondary to prior anticancer therapy (excluding alopecia and peripheral neuropathy) to Grade  $\leq$  1 per NCI-CTCAE

version 5.0 or higher, and complete resolution of immune-related AEs secondary to prior immunotherapy.

- Note: Patients with the following clinically stable or clinically nonsignificant immune-related AEs are permitted: Controlled thyroid disorders, vitiligo, asymptomatic elevated amylase/lipase, type 1 diabetes on insulin, Grade  $\leq 2$  controlled rash, Grade  $\leq 2$  electrolyte abnormalities on stable dose of supplementation.

10. Adequate hematologic function, defined as absolute neutrophil count  $\geq 1.5 \times 10^9/L$ , hemoglobin  $\geq 9.0 \text{ g/dL}$ , and platelet count  $\geq 100 \times 10^9/L$ . Transfusions are permitted to meet hemoglobin and platelet criteria. However, the patient must have a stable hemoglobin level and platelet count for  $\geq 2$  weeks prior to dosing without transfusion.
11. Adequate renal function, defined as serum creatinine clearance  $\geq 30 \text{ mL/min}$  per Cockcroft-Gault formula.
12. Total bilirubin  $\leq 1.5 \times$  upper limit of normal (ULN) ( $\leq 3 \times$  ULN if elevated because of Gilbert's syndrome, and  $\leq 2 \times$  ULN for patients with known liver metastases).
13. Aspartate aminotransferase and alanine aminotransferase  $< 2.5 \times$  ULN ( $< 5 \times$  ULN if liver metastases present).
14. Prothrombin time (PT) or international normalized ratio (INR) and activated partial thromboplastin time (aPTT)  $\leq 1.5 \times$  ULN unless the patient is receiving anticoagulant therapy, in which case PT/INR or aPTT must be within therapeutic range of intended use of anticoagulants.
15. Willingness of male patients who are not surgically sterile to use medically acceptable methods of birth control for the duration of the study treatment period, including 30 days after the last dose of SRF617, 30 days after the last dose of etrumadenant, or 90 days after the last dose of zimberelimab, whichever is later; male patients must refrain from donating sperm for 4 months after the last dose of any study drug. Sexually active men, when having sexual intercourse with a female of reproductive potential, should use an efficient barrier contraceptive (condom plus spermicide); the respective partner should also use an additional efficient contraceptive method (eg, oral pills, intrauterine device, or diaphragm, and spermicide).
16. Ability to adhere to the trial visit schedule and all protocol requirements.
17. Institutional review board/independent ethics committee-approved informed consent form signed and dated by patient (or legally acceptable representative if applicable) before any Screening procedures are performed.

